3.1.2. Recruitment

Participants will be recruited via NHS CHECK and UK REACH cohorts, and via social media and professional contacts and networks. Administrators for the two study cohorts (UK REACH and NHS CHECK) will distribute the online survey to their participants who consented to involvement in future research. The survey will be shared via an email invitation, which contains a link to the REDCap online platform, where the survey will be hosted.

3.1.3. Eligibility criteria

Inclusion criteria:

• UK healthcare professionals whose role involves requesting blood culture samples, taking blood culture samples and/or using the results from blood cultures for adult patients with suspected severe infection.

Exclusion criteria:

- UK healthcare professionals working in neonatal or paediatric acute care or children's emergency department.
- UK healthcare professionals working outside of adult acute care.
- Healthcare professionals working outside of the UK.

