The purpose of this study is to find out why blood culture sampling is not always successfully undertaken. Specifically, we plan to conduct an online survey of UK healthcare professionals to measure their attitudes and beliefs towards blood culture sampling for acute hospital patients with suspected severe infection. We also want to find out what healthcare professionals identify as key barriers to successful blood culture sampling. To obtain representative results that generalise across hospital settings in England, we plan to recruit a national sample of healthcare professionals across different job roles and varying levels of seniority, who are involved in either requesting blood culture samples, taking blood culture samples or using the results from blood culture samples to inform their treatment. This will mean recruiting healthcare assistants, nurses and doctors, amongst other healthcare staff. We will recruit via two established cohorts of healthcare professionals, who previously gave consent to participate in research and provided their contact details for this particular purpose. Up to 400 participants will be recruited from the NHS CHECK and UK REACH cohorts and via social media and professional contacts and networks. Participants will complete an online questionnaire of approximately 20 minutes length. We will analyse the data to identify common attitudes around blood culture sampling and perceived barriers. We will also test whether attitudes differ across different professional roles or clinical settings. Finally, we will test what attitudes and beliefs may predict whether or not healthcare staff engage in blood culture sampling as part of their clinical activities.

This study is part of a wider project that aims to create a bundle of interventions to optimise blood culture sampling practices (IRAS 338495 and 332310).

Study Summary

Study Title	Attitudes and Beliefs around blood culture sampling for treating acute infection
Study Design	Quantitative: online survey
Study Participants	Healthcare professionals responsible for requesting blood culture samples, taking blood culture samples and/or using blood culture test results to inform clinical practice
Planned Size of Sample (if applicable)	400
Follow up duration (if applicable)	N/A
Planned Study Period	14 July 2024 – 30 May 2025
Research Question/Aim(s)	The primary research questions are:

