1 QUESTIONS ABOUT THE PARTICIPANTS

- 1.1 Do you request blood culture samples to be taken for adult patients as part of your regular day-to-day work? Yes/No
- 1.2 Do you take blood culture samples for adult patients as part of your regular day-to-day work? Yes/No
- 1.3 Do you receive results from blood culture samples for adult patients in your regular day-to-day work? Yes/No
- 1.4 Which best describes the clinical setting you currently work in for the majority of your clinical time?

Acute Ward (medical) / Acute Ward (surgical) / Critical Care Unit (HDU or ICU) / Emergency Department / Other acute care setting (please specify) / I do not work in hospital acute care

[Anybody answering "no" to all of the first three questions or "I do not work in hospital acute care" to 1.4 will receive a statement that they aren't eligible for the study and will be directed to an exit page.]

- 1.5 What is your gender? Female/Male/Other/Prefer not to say
- 1.6 What is your age (in years)? years/prefer not to say
- 1.7 How do you describe your ethnicity? White/Mixed or Multiple ethnic groups/Asian or Asian British/Black, African, Caribbean or Black British/Other (please specify)/Prefer not to say
- 1.8 Which best describes your job role? Advanced Clinical Practitioner / Doctor/ Healthcare assistant/ Nurse/ Paramedic/ Phlebotomist/ Physician's Associate / Other (please specify) /Prefer not to say
- 1.9 A: For doctors only: What is your career stage? FY1/FY2/CT1/CT2/CT3/ST4+/Consultant/Other (please specify)/Prefer not to say
 B: For nurses/HCAs only: What is your current grade? Band 3/Band 4/Band 5/Band 6/Band 7/Band 8/Band 9/Other (please specify)/Prefer not to say
 C: APCs only: What is your current stage of training? Trainee / Qualified / Credentialled/Other (please specify)/Prefer not to say

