4 QUESTIONS ABOUT FACTORS THAT AFFECT BLOOD CULTURE SAMPLING

Below is a list of factors that have been suggested as barriers to blood culture sampling for adult patients with suspected severe infection. Please rate to what extent you agree that these factors influence current blood culture sampling practices in acute hospital care in England. There is also an option to include additional factors that you have identified based on your professional experience. Please add as many factors as you consider relevant.

- 1 = Strongly disagree [that this factor influences blood culture sampling]
- 2 = Disagree [that this factor influences blood culture sampling]
- 3 = Somewhat disagree [that this factor influences blood culture sampling]
- 4 = Neither agree or disagree [that this factor influences blood culture sampling]
- 5 = Somewhat agree [that this factor influences blood culture sampling]
- 6 = Agree [that this factor influences blood culture sampling]
- 7 = Strongly agree [that this factor influences blood culture sampling]

[The list of factors will be presented in randomised order to each participant.]

Barriers to requesting blood culture samples

- 4.1 Staff forget to request blood culture samples.
- 4.2 The request to collect a blood culture sample is not always communicated to staff who need to take the sample.

Barriers to collecting blood culture samples

- 4.3 Staff forget to take blood culture samples that have been requested.
- 4.4 Staff find it unpleasant to take blood culture samples.
- 4.5 It is technically difficult to obtain blood culture samples (e.g., due to difficulties with canulation).
- 4.6 Staff are insufficiently skilled or experienced in taking blood culture samples.

4.7 Blood culture kits (bottles, needles, syringes) are not easily available.

Barriers to packaging, storing and transporting samples

- 4.8 There is insufficient knowledge about storage requirements for blood culture samples.
- 4.9 There is insufficient knowledge about the prevention of contamination throughout all stages of blood culture sampling.
- 4.10 Blood samples get delayed during transfer to the laboratories.
- 4.11 Blood samples get lost during transfer to the laboratories.
- 4.12 The location of the nearest microbiology laboratory is inconvenient (e.g., too far away).

Barriers to laboratory testing of blood culture samples

- 4.13 There are concerns about the financial costs of doing too many laboratory tests.

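### The Part 1b survey excludes staff working outside the UK but records no country or UK nation, and its barrier section asks a UK-wide sample about practice in England

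*Protocol*

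**What the plan says.** Part 1b, section 3.1.3 (Eligibility criteria) admits "UK healthcare professionals whose role involves requesting blood culture samples, taking blood culture samples and/or using the results from blood cultures", limited to the care of adults in whom severe infection is suspected. One of its three exclusions is "Healthcare professionals working outside of the UK".

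Section 3.1.2 (Recruitment) states: "Participants will be recruited via NHS CHECK and UK REACH cohorts, and via social media and professional contacts and networks".

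Appendix A, section 1 opens with three yes/no items on requesting, taking and receiving results from cultures in adult patients. Item 1.4 then asks "Which best describes the clinical setting you currently work in for the majority of your clinical time", and its answers are types of unit. Anyone who answers no to all three opening items, or who reports at 1.4 not working in hospital acute care, "will receive a statement that they aren't eligible for the study and will be directed to an exit page". The remaining items cover gender, age, ethnicity, job role and grade.

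The stem of Appendix A, section 4 asks how far the respondent agrees that "these factors influence current blood culture sampling practices in acute hospital care in England".

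The Part 1b short lay summary gives the purpose of the national sample: "To obtain representative results that generalise across hospital settings in England". The same summary describes a survey of UK staff. The Background (section 1) and Study Design (section 3) of Part 1b describe the sample as UK healthcare professionals, and the research questions refer to NHS healthcare professionals.

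**The concern.** There are two separate problems.

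- **An exclusion with nothing to apply it.** If country of work is neither asked nor stored, the non-UK exclusion depends on respondents excluding themselves. Any who do not would be carried into every analysis: the factor analysis, the ANOVAs, the regressions and the barrier summaries.
- **A question that does not match the population.** A clinician in Scotland, Wales or Northern Ireland is properly eligible but is asked in section 4 about England. That person may rate England from outside or may rate the home system, and the two kinds of answer are then pooled.

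The analysis plan ranks the three most influential barriers overall and also ranks barriers by role and by setting. Section 3 (Theoretical Framework) of the Part 1c and Part 2 protocol uses barriers from the survey to build the co-design tools. What is at stake is whether those rankings can be tied to a defined population.

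**Working it through.** The protocol states no figure on this point, so there is none to reproduce. The check is mainly a comparison of passages.

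**1. Is each exclusion matched by a screen?**

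| Exclusion (Part 1b, 3.1.3) | Counterpart in Appendix A, section 1 |
|---|---|
| Neonatal or paediatric acute care, or children's ED | Partial: items 1.1 to 1.3 specify adult patients |
| Outside adult acute care | Items 1.1 to 1.3, and the last answer option at 1.4 |
| Outside the UK | None |

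The exit rule uses items 1.1 to 1.4 only. Some titles and grades in items 1.8 and 1.9 are specific to the UK, but the options for doctor, nurse, other and prefer not to say leave the path open to a respondent abroad.

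**2. Could the exclusion be applied at analysis?** Item 6 of the Part 1b analysis plan excludes on completion time, on missing attitude items and on straight-lining. Section 3.1.4 adds completion of less than half the questionnaire. None of these uses country. Section 3.1.4 also says that no names, email addresses or identification numbers are kept with the responses, so country cannot be recovered by going back to the person.

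**3. Which geography applies where?**

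| Place in Part 1b | Geography |
|---|---|
| Background, Study Design, Eligibility criteria | UK |
| Research questions | NHS staff, no nation named |
| Appendix A, section 4 stem | England |
| Short lay summary | UK staff surveyed, England as target |

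Two geographies are in use, UK and England. Because nation is not recorded, the section 4 ratings cannot be split by it.

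**4. Illustrative size.** Let c be the share of respondents in one affected group and d the difference between their mean rating of a barrier and that of everyone else. The pooled mean is (1 − c)μ + c(μ + d) = μ + c·d, so the shift is c·d. The documents give neither c nor d. I assume c from 2% to 20% and d from 0.5 to 2 points on the 7-point scale. The planned maximum of 400 respondents is taken before any exclusions.

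| c | People (400 × c) | Shift at d = 0.5 | Shift at d = 2 |
|---|---|---|---|
| 2% | 8 | 0.01 | 0.04 |
| 5% | 20 | 0.025 | 0.10 |
| 10% | 40 | 0.05 | 0.20 |
| 20% | 80 | 0.10 | 0.40 |

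The formula applies separately to ineligible non-UK respondents and to eligible UK respondents outside England. These groups have different standing and should not be added together. The lower end of the range is negligible. The upper end could reorder barriers whose means lie close together.

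**The case against.** The case on the other side has real force on several points.

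- **The consent page is not visible.** Section 3.1.4 places an information sheet and e-consent form on the landing page, and nobody proceeds without agreeing to its items. Those items are not shown and may state the UK restriction. A reader might infer that a nurse abroad would meet no barrier at all, or that ineligible answers certainly enter. The documents do not support either. What stands is that a statement on that page would work by self-selection, with no country in the recorded data as shown.
- **The main sources appear UK-based.** Judging by their names, the two cohorts are UK cohorts, and their administrators email the invitations. Non-UK entry is plausible mainly through the open route, "and via social media and professional contacts and networks", whose share is not given.
- **England is not clearly the inferential target.** A reader might infer that staff elsewhere in the UK contaminate an England study and that eligibility or primary reporting should be limited to England. Only the lay summary names England as the target. The research questions and design are NHS- and UK-wide, so these staff belong to the intended population. The fault lies in the section 4 stem and one lay-summary sentence.
- **The attitude items are largely unaffected by the England wording.** Appendix A, section 3 asks about the respondent's own role, unit and colleagues, so eligible staff outside England can answer validly. Only non-UK respondents, if any, would affect those results.
- **The effect may be trivial.** This is accepted. The shares above are assumptions, and the barrier analysis is descriptive.

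**Conclusion.** The point holds as two limited defects. First, the non-UK exclusion cannot be enforced or checked from the questionnaire and exclusion rules as printed, so non-UK responses can enter and could not then be found or removed. Second, the section 4 stem asks about England while the eligible population is the whole UK, so what eligible staff in the other three nations rated cannot be known. The second defect exists even if nobody abroad responds.

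The size of any effect on the barrier rankings is unknown. Under the assumed shares and differences, a barrier mean moves by between 0.01 and 0.40 points. The conclusion does not depend on those numbers: as designed, any such bias can be neither measured nor corrected. This is a cheap improvement to make. It does not invalidate the survey.

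**What to change.** - Add one item to Appendix A, section 1 on nation of main work, with the answers England, Scotland, Wales, Northern Ireland and outside the UK.
- Extend the exit rule so that the last answer leads to the existing exit page.
- Reword the section 4 stem to refer to the respondent's own workplace, or to the UK.
- Keep the UK-wide sample as the main analysis, with England available as a breakdown.
- Align the lay-summary sentence on generalising to England with the UK population.

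The cost is one extra question and an amendment to an instrument that Part 1b describes as piloted and whose protocol it describes as ethically approved. The analysis plan says no data had been collected, but the Part 1b protocol is dated 25 June 2024, the planned period starts on 14 July 2024 and the combined protocol carries the date 22 July 2024. Collection may therefore have begun. If it has, the change applies from its date of introduction, and the limitation should be reported for earlier responses.

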3.1.4. Consent and withdrawal

A participant information sheet (PIS), privacy notice and e-consent form will be integrated within the landing page of the online survey. Only if participants agree to the items on the consent form and indicate their agreement via a tick box can they proceed to the next stages of the survey. The PIS will provide an email address, which they can contact in case of questions. Participants can take as long as they like to decide whether they want to take part, although the survey will be closed once the maximum number of participants has been recruited. Participants will have the option to provide their name and email address and can indicate whether they would like to receive an electronic summary of the study results and/or be entered into a prize draw.

Participants will be informed in the PIS that they can withdraw during the participation by closing the online questionnaire. Their data will not be included in the analysis if they complete less than half of the questionnaire. It will not be possible to withdraw participant data after the questionnaire is completed. This is because individual questionnaire responses will not be identifiable, because no names/email addresses/identification numbers will be stored alongside the research data.

4. Methods of data collection

We will use a newly developed and piloted questionnaire (Appendix A) informed by the Theory of Planned Behaviour (16, 17). The questionnaire contains 3 questions to measure self-reported levels of (1) requesting blood culture samples, (2) taking blood culture samples and (3) using the results from blood culture samples. This is followed by 20 questions pertaining to attitudes and beliefs around blood culture sampling and 30 items listing potential barriers to blood culture sample, which were informed by a literature research and hospital stakeholder visits. All items will require rating, using likert-scales. The questionnaire will conclude with a final open-ended question asking for suggestions about potential interventions to improve blood culture sampling.

4.1. Data analysis

Data analysis will involve quantitative methods, including: (1) descriptive statistics of beliefs and perceived barriers to blood culture sampling, rated on likert scales; (2) confirmatory factor analysis to test the hypothesized factor structure of our newly developed questionnaire; (3) Analysis of variance (ANOVA) to test for interactions and effects of professional roles and clinical setting on attitude ratings regarding blood culture sampling; (4) multiple regression analyses to identify predictors or self-reported engagement in the blood culture pathway, and (5) qualitative content analysis of an open-ended question around potential interventions to improve blood culture sampling. The full analysis plan can be found as Appendix B.

4.2. Access to data

Before the study starts, only the administrators of the two study cohorts will have access to names and email addresses of individuals, who have previously agreed to participate in

research. During the study, the immediate research team will have access to the names and email addresses of participants, who provided contact details to receive result summaries or be entered into the prize draw. This data will not be transferred to external collaborators. The study research team will also have access to the de-identified research data (including demographic details and attitude ratings). These de-identified data will be shared with project collaborators at RAND Europe for analysis and may be deposited on Open Science Framework data repository. Consent will be sought from participants to do so.

5. Ethics

Individuals invited to participate in the survey will be provided with full study information and informed that participation is voluntary. Consent to participate will be obtained via the landing page of the survey to which participants will affirm their consent before entering the survey. Participants are not required to give their name or any personal information for completion of the online survey, unless they wish to receive a study summary or enter a prize draw to win a £50 shopping voucher, in which case they can leave their name and contact details at the end of the survey. This personal information will be stored separately from their main research data in a password protected file on the University of Leicester's secure drive. After sharing the study summary, this data will be destroyed.

In addition to these optional identifiable data, we will collect some personal data, which is required to obtain statistics about sample diversity and which will be used for some of the analyses. These personal data include age, gender and ethnicity. For all of these items, participants will have the option to select "prefer not to specify". Fully anonymised survey data will be shared with project collaborators from RAND Europe for analysis, stored on the University of Leicester servers for at least six years, and shared via the Open Science Framework research repository, in line with open science good practice.

The survey involves the completion of a short online survey about beliefs and attitudes about blood culture sampling. Blood culture sampling will be a usual or routine part of the participants' clinical role. We do not envisage there to be any adverse effects, discomfort or distress. Completion of the survey is entirely voluntary. Participants can withdraw during the survey.

Participants might find it interesting and valuable to participate in this research project and share their views on blood culture sampling. They will be contributing to the wider project's co-design process to create a bundle of interventions to optimise blood culture sampling practices in acute care for patients with suspected severe infection. They might enjoy receiving a summary of the results, which will provide insights into fellow healthcare workers' attitudes and the overall project. Additionally, a potential benefit is the chance to win a £50 shopping voucher to thank them for their time.

The study will be submitted for approval by the University of Leicester Research Ethics Committee.

6. Patient and public involvement

We convened a PPI group for the wider study comprising 7 individuals with experiences of severe infection and hospital care to advise on the study design. This PPI group reviewed and provided feedback on a survey draft via email. They commented on the general acceptability, length, and wording of questions asked. The PPI group will also be involved in

the interpretation and dissemination of results. Methods training will be provided for this purpose.

7. Dissemination

Survey results will be disseminated via conference presentation, our research group's X (Twitter) feed, as an open access peer reviewed journal article, and as part of the formal report to funder. Publications and outputs will be available on open access via the University of Leicester's library database/repository.

Participants can opt in to receive a summary of the study results. Should they wish to obtain results, they may enter their email address for this particular purpose. We will store this information separately from their data and use it for the sole purpose of sending the results summary. After sharing the summary, this data will be destroyed.

APPENDIX A – Survey about healthcare professionals' beliefs and attitudes towards blood culture sampling

